Impact of the COVID-19 pandemic on emergency department attendances and admissions in Southampton for children and young adults

Investigators

[name], Paediatric Allergy and Respiratory Medicine University of Southampton, Southampton, UK

[name], Research assistant, University Southampton, Southampton, UK

Collaborators

[name], Consultant in Paediatric Emergency Medicine, University Hospital Southampton NHS Foundation Trust, Southampton, UK

[name], Consultant in Paediatric Emergency Medicine, University Hospital Southampton NHS Foundation Trust, Southampton, UK

[name], Paediatric Registrar, Wessex Education Deanery, UK

Additionally, [name] (a final year medical student at University of Southampton) who is currently attached to [name] group will be assisting with the analysis of the project data.

Project aim

To assess the ongoing impact of the COVID-19 pandemic on attendances by children and young adults to the emergency department and admissions to the hospital.

Objectives:

1. Assess the impact of the pandemic on overall (a) emergency department attendances and (b) hospital admissions for 0 to 4, 5 to 10, 11 to 17 and 18 to 24 year groups.
2. Assess the impact of the pandemic on (a) emergency department attendances and (b) hospital admissions for specific medical, surgical, trauma and mental health conditions for 0 to 4, 5 to 10, 11 to 17 and 18 to 24 year groups.

Background

The COVID-19 pandemic has had a major impact on healthcare utilisation and delivery for children and young adults. This is despite them experiencing minimal morbidity and almost no mortality as a direct result of the pandemic (Docherty 2020). The immediate impact of the first lockdown in April 2020 has been well documented. A number of studies show a marked reduction in presentations of children and young adults to the emergency department (Dann 2020; Isba 2020; Roland 2020).

The question is now, are these trends continuing and are they particularly impacting on specific groups and on specific presentations? With these data, services can be modified to minimise any potential for deleterious effects. It may also be possible to target groups who are not utilising health services as we would expect.

Study design

This project will analysis an anonymised database from retrospective electronic medical records of participants who presented or been admitted to University Hospital Southampton NHS Foundation Trust.

Participants

Children and young adults aged 0 to 24 years who have presented +/- admitted to the emergency department at University Hospital Southampton NHS Foundation Trust between the 1st of April 2016 and 31st of March 2021.

Data to be used in analysis

This project we use an anonymized data set meaning that it will contain no identifiable data (including but not limited to name, date of birth, hospital number, NHS number, address). The anonymized dataset will be provided by [name] who is a consultant paediatrician at University Hospital Southampton NHS foundation trust and is a collaborator on the study. Prior to anonymisation, postcode data will be used to generate a deprivation score for participant via their Office of National Statistics (ONS) small area code (Office National Statistics).

Data used in the project will include calender week of presentation/admission, age in complete years (rounded down), gender, ethnicity, refer (eg self, ambulance, GP, 111), presenting/discharge diagnosis, deprivation decile and re-attendance.

Outcomes

Attendance at the emergency department in Southampton defined as being booked onto the emergency department admission system. Participants will be divided into the following age groups: 0 to 4, 5 to 10, 11 to 17 and 18 to 24 years.

As well as all attendance, we will also look specifically at a number of subgroups. These will depend on the diagnostics labels attached to the data. It is expected that they will be:

- Respiratory infection, e.g. bronchiolitis, chest infections, pneumonia,
- Asthma and wheeze
- Gastrointestinal, E.g. gastroenteritis, vomiting
- Surgical, E.g. appendicitis, intestinal obstruction
- Mental health, e.g. overdose, self-harm
- Accidental injuries/trauma
- Non-accidental injury or safeguarding
- Diabetes

Admission to University Hospital Southampton NHS Foundation Trust defined as being in hospital for more than four hours. Participants will be divided into the same subgroups as per attendances.

Potential explanatory variables

These are factors that might explain differences between different participants in the study. They are:

- calendar week of presentation/admission - it is expected that the data will be seasonal.

- age in complete years - it is expected that patterns will differ for the different age bands.
- gender - it is possible that patterns will vary by gender.
- ethnicity - it is possible that patterns will vary by ethnicity.
- deprivation decile - it is possible that patterns may vary by participants social economic status. This will be indicated by their ONS deprivation decil.

Approach to analysis

Graphical presentation of data

The data for presentation and admission will be separately presented by graphical and/or tabular means. For each age band overall number of presentations/admissions will be presented for each calendar week from April 2016 to March 2021. This will be repeated for each of the presenting and discharge diagnoses listed above. Further graphs will be presented looking at male and female participants, white and non-white participants and deprivation decils 1-3, 4-7 and 8-10 separately. Figures will be annotated with key events e.g. first COVID-19 case in the UK, first death in the UK, lockdown periods and imposition of different levels plus dates of key local pathway changes (eg opening of new children emergency department (December 2018) and movement of paediatric assessment unit to the emergency department (September 2019).

Interrupted time series regression analysis

To assess the impact of the pandemic on presentations in admissions, an interrupted time series regression analysis will be undertaken using Stata (version 16). The primary analysis will focus on the total attendances and admissions. The various subgroups will represent exploratory analyses. A single group comparison will be used looking at the trend in presentations and admissions before and after the March 2020 lockdown. Given the expected number of presentations and admissions, data will be groups into four week time periods (13 in each calendar year).

Using this time series regression analysis approach we will control for seasonality and also assess whether gender, ethnicity or deprivation influence any change in presentation or admissions. A p-value of less than 0.05 will be taken to indicate statistical significance.

Sample size analysis

There are no established approaches to undertaking a power analysis for an interrupted time series. A scoping review (Ewusie 2020) suggests that “24 or more time points have more than 80% power to detect an effect size of 1 or greater” and “that a minimum of 8 time points per period is required to gain sufficient power in estimating the regression coefficients”. With five years of data and 13 4-weekly blocks per year, we have 65 time points, 12 of which will be after the first lockdown. In total, we expect to have around 2000 attendance and 400 admissions in each four week block for the primary analysis. This is expected to provide at least 80% power for the primary analysis. For specific conditions, number are likely to be smaller; for example, there may be around 50 attendances for mental health conditions in each four-week block.

Ethical and research governance considerations

This project uses routine clinical data which will be anonymized prior to its use by the research team. It therefore just falls outside the General Data Protection Regulations. Under the current research governance framework, it is also exempt from research ethics committee assessment (Health Research Authority). However, as it involves the utilisation of data from

NHS patients, it needs to be assessed by the Health Research Authority. It also requires an assessment by the faculty of medicine research ethics committee at the University of Southampton.

Planned dissemination

The results will be presented locally in Southampton and the Wessex region to inform the local stakeholders. Additionally, one of more publications will be submitted, eg abstract to a national meeting and/or a manuscript to a peer review journal. Authorship for these will follow the International Committee of Medical Journal Editors recommendations, in brief substantial contributions to the conception or design of the work, or the acquisition, analysis, or interpretation of data for the work; drafting the work or revising it critically for important intellectual content; final approval of the version to be published; and agreement to be accountable for all aspects of the work in ensuring that questions related to the accuracy or integrity of any part of the work (ref International Committee of Medical Journal Editors).

References

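### Two dated pre-lockdown pathway changes are marked on figures only; one sensitivity fit should show whether the March 2020 estimates depend on them (minor)

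*Protocol*

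**What the plan says.** Under Graphical presentation of data, the protocol says that figures will be annotated with national events and with "key local pathway changes (eg opening of new children emergency department (December 2018) and movement of paediatric assessment unit to the emergency department". The second of these is dated September 2019. No other use of the two dates is stated.

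Under Interrupted time series regression analysis: "A single group comparison will be used looking at the trend in presentations and admissions before and after the March 2020 lockdown". The adjustments named are seasonality and an assessment of gender, ethnicity and deprivation. The same section says "The primary analysis will focus on the total attendances and admissions".

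Under Outcomes, attendance is set by a booking event: "Attendance at the emergency department in Southampton defined as being booked onto the emergency department admission system". Admissions are set by length of stay: "Admission to University Hospital Southampton NHS Foundation Trust defined as being in hospital for more than four hours".

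The Background regards the early fall as established ("The immediate impact of the first lockdown in April 2020 has been well documented") and asks what followed: "are these trends continuing and are they particularly impacting on specific groups and on specific presentations".

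**The concern.** An interrupted time series without a control series takes its no-pandemic expectation from the pre-lockdown data. If something else changed the count during that period, and the model has no term for it, a trend fitted to the whole baseline absorbs part of the change and carries it past March 2020.

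The protocol itself names two candidates. The September 2019 move is the more worrying. It brought an assessment unit into the ED shortly before lockdown, and the outcome depends on who is booked onto the ED system. Children could enter the attendance count because the route changed and not because more families sought care. An upward step would hide part of a later fall; a downward one would exaggerate it.

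A large first-lockdown fall would survive. What is exposed is its size and the trend afterwards, which is the question the Background says is still open.

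**Working it through.** **The protocol's own figures.** Five years of 13 blocks give 5 × 13 = 65 time points, as stated. With 12 after lockdown ("we have 65 time points, 12 of which will be after the first lockdown"), 65 - 12 = 53 lie before it.

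**Dates to blocks.** These are 28-day blocks counted from 1 April 2016, the start of the data window.
- Block 35 runs from 9 November to 6 December 2018, so a December 2018 change first appears in block 35 or 36.
- Block 45 runs from 16 August to 12 September 2019, so a September 2019 change first appears in block 45 or 46.
- Block 52 runs from 28 February to 26 March 2020, and block 53 from 27 March to 23 April 2020.

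Twelve post-lockdown blocks put block 53 before lockdown. The protocol dates the first lockdown to March 2020 in the analysis section and to April 2020 in the Background. I therefore ran both 53 and 52 pre-lockdown blocks. Between 7 (blocks 46-52) and 9 (blocks 45-53) blocks lie between the September 2019 change and lockdown.

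**Assumed model.** The protocol gives no equation. With p pre-lockdown blocks, m = 65 - p, and P = 1 after lockdown:

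y = b0 + b1·t + b2·P + b3·P·(t - p - 1) + b4·sin(2πt/13) + b5·cos(2πt/13), with independent errors.

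The level change is b2 and the slope change is b3. The average post-lockdown effect is b2 + b3·(m - 1)/2.

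**Bias from an unmodelled step.** If S is the 0/1 step and d its size, the bias is d·(X'X)⁻¹X'S.

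| Unmodelled step | Level change | Slope change per block | Average effect |
|---|---|---|---|
| September 2019 | +0.47d to +0.62d | -0.025d to -0.030d | +0.32d to +0.46d |
| December 2018 | about 0 | -0.026d to -0.034d | -0.15d to -0.19d |
| Both, same size and direction | +0.46d to +0.62d | sum of the two | +0.13d to +0.31d |

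Lower September value: p = 53, step from block 45, 0.466 - 0.026 × 5.5 = 0.323. Upper: p = 52, step from block 46, 0.620 - 0.027 × 6 = 0.458. With both steps, the average-effect biases partly cancel.

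**In counts.** The protocol expects about 2000 attendances per block. The step sizes below are assumptions.
- d = 100 (5%), September alone: level +47 to +62; average +32 to +46 per block (1.6-2.3% of 2000).
- d = 200 (10%), September alone: level +93 to +124; average +65 to +92 per block (3.2-4.6%).

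**Against sampling error.** The standard error of the average effect is about 0.44 residual SD. For d = 100 and an assumed residual SD of 100, the standard error is about 44 and the bias is 32/44 = 0.7 to 46/44 = 1.05 standard errors. At an assumed SD of 200 the bias is about half a standard error or less.

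**With two step indicators added.** An exact step at the assumed dates then leaves no bias. The standard error of the level change, in residual SD units, rises from 0.656 to 0.696-0.717 with 53 pre-lockdown blocks (6-9%), and from 0.634 to 0.690-0.714 with 52 (9-13%).

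**The case against.** The strongest objection is that this is a missing sensitivity analysis, and such analyses often sit in a statistical analysis plan, which is not at hand. The word single in the regression section qualifies the group, meaning no control series. It does not limit the number of change points, and the protocol gives no closed list of terms. Step terms would contradict nothing in it. The authors have already identified both events and will mark them on weekly plots by age band, where a large step would show.

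Much of this stands. A reader might infer that the protocol rules out adjustment for these events, or that they did distort the baseline. The text supports neither. It gives no size, sign or evidence of a step. It does not say whether assessment-unit children were already booked on the ED system before September 2019; if they were, that move need not change the count. Both changes concern children's services, so ages 18 to 24 would dilute any step in the total series.

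What remains is that the protocol calls these changes key, dates them, and then states a graphical role for them alone beside a before/after comparison that would be biased if a step occurred. A marked figure can reveal a step. It cannot say how far the March 2020 estimate depends on it.

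Admissions may look safe because they are defined by length of stay. However, participants are those who presented to the ED, with or without admission, so the move could also affect who enters that series. The protocol does not settle this.

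**Conclusion.** The point holds as a minor one. If the September 2019 move shifted attendances by d, the stated comparison would misplace the March 2020 level change by roughly half of d (+0.47d to +0.62d) and the average post-lockdown effect by about a third to just under a half of d. A December 2018 step would bear mainly on the slope change. These multiples rest on the assumed segmented form, one harmonic, independent errors and an abrupt step; d itself is unknown and may be zero.

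A reader might go further and infer that the pandemic effect itself could be an artefact of the pathway changes. The protocol does not support that. Its Background reports a marked reduction in presentations already documented elsewhere, and a bias of a few percent of the block count would not create or conceal a large fall. The exposure is in the estimated size and in whether a smaller deficit persisted.

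**What to change.** In the interrupted time series section, keep the planned model as primary. Add one prespecified sensitivity analysis for total attendances and admissions, with the under-18 age bands as exploratory, that includes a 0/1 step indicator from December 2018 and another from September 2019. Report the March 2020 level and slope changes from both fits side by side. A note on whether assessment-unit children were booked on the ED system before September 2019 would help readers interpret any difference.

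The text needs a sentence or two, and the dates are already in the protocol. The statistical cost falls on the sensitivity fit only: the standard error of the level change rises by about 6-13%, that of the average effect by 10-18%, and that of the slope change by 2-3%. The September step rests on only 7-9 blocks, mostly autumn and winter, so it is weakly separated from season and from the lockdown itself. Step terms also do not fully remove a gradual change: a ramp over 8 blocks from September 2019 would leave 0.37-0.49 of its size in the average effect, against 0.58-0.72 without them. The second fit is therefore a check on the primary model and not a replacement for it.

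### Should 13 rather than 12 of the 65 four-week time points fall after the March 2020 lockdown?

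*Protocol*

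**What the plan says.** The Participants section takes attendances "between the 1st of April 2016 and 31st of March 2021". The Interrupted time series regression analysis section compares trends "before and after the March 2020 lockdown" and says that "data will be groups into four week time periods (13 in each calendar year". The Sample size analysis section starts from "With five years of data and 13 4-weekly blocks per year" and concludes that "we have 65 time points, 12 of which will be after the first lockdown". It sets these counts against a cited scoping review, which asks for at least 24 points in all and says that "a minimum of 8 time points per period is required to gain sufficient power".

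Two other places bear on the count. Under Data to be used in analysis, time is recorded only as a week: "Data used in the project will include calender week of presentation/admission". The Background gives a different month for the same event: "The immediate impact of the first lockdown in April 2020 has been well documented".

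The protocol does not give the day in March on which the break falls, the date from which blocks are counted, or what happens to a block that contains the break.

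**The concern.** The total and the split seem to follow different rules. If a year is 13 blocks, the five study years give 65, the four years before April 2020 give 52, and the last year gives 13. The protocol keeps the 65 but reports 12 after, which leaves 53 for everything else.

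This is the only statement of how the series divides, and in a single-group before-and-after design the break defines the effect being estimated. An analyst who read the sentence as 53 before and 12 after could code the first lockdown block as pre-pandemic. That block would pull the fitted pre-lockdown line towards the lockdown level and shrink the estimated step. The March and April datings add to the doubt about where the break lies.

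**Working it through.** **Inputs.** Window 1 April 2016 to 31 March 2021 (Participants); four-week blocks, 13 a year, and a March 2020 break with no day given (Interrupted time series regression analysis); 65 points with 12 after, minimum 8 per period and 24 in total (Sample size analysis).

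**Step 1. The protocol's total.** 5 × 13 = 65, reproduced. By dates, the window is 1,826 days, and 1,826 / 28 = 65.2 blocks.

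**Step 2. The nominal split.** 4 × 13 = 52 before and 1 × 13 = 13 after. This puts the break at the turn of March and April 2020, which the protocol does not state either.

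**Step 3. The split by dates.** Every break date from 1 to 31 March 2020 was tried, counting whole blocks that start on or after the break. In grids that restart each year, the thirteenth block absorbs the spare days.

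| Block grid | Whole blocks in window | Whole blocks after the break |
|---|---|---|
| Run from 1 April 2016 | 65 | 13 for 1–27 March; **12 for 28–31 March** |
| Restarted each 1 January | 64 | 13 for 1–25 March; **12 for 26–31 March** |
| ISO weeks, restarted yearly | 64 | 13 for 1–23 March; **12 for 24–31 March** |
| Restarted each 1 April | 65 | 14 for 1–2 March; 13 for 3–31 March |
| Counted back from 31 March 2021 | 65 | 14 for 1–5 March; 13 for 6–31 March |

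Two examples show where the 12 comes from.

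- **Run from 1 April 2016.** Block 53 starts 52 × 28 = 1,456 days later, on 27 March 2020. A break on 28 March falls inside it, giving 52 before + 1 split + 12 after = 65, which matches both of the protocol's figures.
- **Restarted each 1 January.** The fourth block of 2020 starts on 25 March. After it come blocks 5 to 13 of 2020 (9) and blocks 1 to 3 of 2021 (3), and 9 + 3 = 12. Before it come 9 whole blocks in 2016, 3 × 13 = 39 in 2017 to 2019, and 3 in 2020, which make 51. The split is 51 + 1 + 12 = 64.

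**Step 4. Do weekly data rule out 12?** No. On the yearly ISO-week grid, which uses whole calendar weeks, a break at the week starting Monday 30 March 2020 gives 51 + 1 + 12. On a continuous grid of Monday-start weeks from 4 April 2016, the same break gives 52 + 13.

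**Step 5. The power rationale.** On these grids the whole blocks after the break number 12 to 14, against a minimum of 8. Even with a split block left out, the smallest total is 51 + 12 = 63 (or 50 + 13 = 63), against a minimum of 24.

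**Step 6. Precision.** In a plain segmented regression with independent errors and no seasonal terms, the standard errors in residual SD units are:

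| Split | Level change | Slope change (per block) |
|---|---|---|
| 52 + 13 | 0.5949 | 0.0747 |
| 53 + 12 | 0.6103 | 0.0841 |
| 52 + 12, one block left out | 0.6154 | 0.0841 |

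Moving from 13 to 12 blocks after the break raises the standard error of the level change by 0.6103 / 0.5949 = 1.026, about 3%, and that of the slope change by 0.0841 / 0.0747 = 1.126, about 13%. Where 13 blocks are in fact available, planning on 12 is the cautious figure.

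**The case for a change.** The best argument for a change is that the protocol chose to state the split, so the split should follow from its own inputs. Twelve does so only with a split block that is never mentioned. No March date on these grids leaves 53 whole blocks before the break, so a literal 53 and 12 cannot be right.

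Miscoding would also have a cost. Take a noise-free step fitted by least squares with intercept, trend, level change, slope change and one annual harmonic. If block 53 is fully exposed to lockdown, a 53/12 coding recovers 0.917 of the level change. If block 53 is half exposed, coding it as before gives 0.959, coding it as after gives 0.849, and leaving it out gives 1.00. One sentence and one date would remove the doubt.

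Part of this stands: the count is unexplained, and a split block does need a decision. The rest does not carry a change. The protocol says that 12 points come after the lockdown; it does not say that 53 come before, and it proposes no 53/12 model. The ratios therefore describe a coding that the protocol never adopts. Nor can a correct pair of counts be written in from the document alone. A break on a block boundary gives 52 + 13 on the grid from 1 April 2016 but 51 + 13 on the calendar-year and ISO grids. Leaving out the split block gives 52 + 12 on the first and 51 + 12 on the others. The counts follow once the analyst fixes the grid and the date.

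The April wording is weak support. It stands in the Background, introduces published studies, and can be read as the impact seen in April. The analysis section sets the break in March.

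**Conclusion.** The figure of 12 is unexplained, but the document does not show it to be wrong. It is the correct number of whole blocks after a late-March break on three natural grids, and on one of them it sits alongside exactly 65 blocks. The nominal 13 rests on an unstated convention of its own.

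The discrepancy is one block against the nominal split, or two at most on the grids tried. It does not alter the protocol's power rationale, whose thresholds of 8 per period and 24 in total are met on every count, and it costs little precision for the level change. What is left open (the day of the break, the block origin and the handling of a split block) is block construction that an analyst settles when coding the model and that an analysis plan would commonly hold. No change to the plan follows.

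This rests on three assumptions: the break lies somewhere in March 2020, as the analysis section says; the five grids cover the sensible ways to form the blocks; and the precision figures assume independent errors. Whether the cited thresholds are themselves a sound basis for the power claim is a separate question, not examined here.
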